7.6 Allowable Therapies

Usual care will be provided throughout the trial to all participants. Details of usual care received will be recorded in the CRF during trial visits. Usual care includes any intervention that would ordinarily be offered out-with the trial setting.

Usual care includes, but is not limited to, oral corticosteroids, inhaled or nebulised bronchodilators, mucolytic therapy, and pulmonary rehabilitation.

8 Trial Investigation of Medicinal Product (IMP)

8.1 IMP supply, storage and Dispensing

Azithromycin will be supplied from pharmacy stock and stored in ambient temperature conditions within the drug cupboard. Azithromycin will be standard treatment for the participants as prescribed by the treating clinician.

8.2 Dosing of IMP

The dosage for Azithromycin will be as per common treatment regimens and be administered orally.

9.1.1 Reporting Adverse Events

All adverse events will be reported in accordance with HUTH R&D department's Safety Reporting standard operating procedure (R&D GCP SOP 07) to ensure compliance with UK Clinical Trial Regulations. All SUSARs relating to Azithromycin will be reported to the competent authority/authorities using the SUSAR reporting routes.

9.1.2 Adverse Event reporting period

The AE reporting period for this trial begins when the participant has consented to the trial and ends at the participant's final trial visit. Each trial participant will be questioned about adverse events at each visit and the trial team will examine medical records at each visit to identify any AEs that may have occurred. The investigator will record all directly observed AEs and all AEs spontaneously reported by the trial participant. A pre-existing condition (i.e. a disorder present before the AE reporting period started and noted on the pre-trial medical notes), is not to be reported as an AE unless the condition worsens or episodes increase in frequency during the AE-

reporting period. All adverse events (serious and non-serious) will be recorded in participants data collection forms (CRFs) using the adverse event report form. All adverse events will be recorded in participants' medical records. All AEs will be followed-up until the event has resolved or a decision has been taken for no further follow-up.

However, if a patient provides informed consent but is subsequently found to be ineligible, then the reporting period will end at the point that the decision was made that the patient was ineligible.

Where a participant withdraws consent for further processing of data, this does not preclude the reporting of SARs and SUSARs which are required to continue being reported according to the protocol for regulatory purposes.

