4.2 Exclusion Criteria

- Previous treatment with long-term macrolides in the past 3 months.
- Unable to be investigated with HROM due to contraindications such as anatomical abnormalities or diseases of the oesophagus or unwilling/ unable to be investigated with HROM based on the clinical judgement of the investigators due to severity of lung disease.
- Have another cardiorespiratory cause for their symptoms (such as heart failure or lung cancer).
- Are unable or unwilling to consent to or complete the trial procedures
- Women of child bearing potential not using effective means of contraception. Effective methods
 of contraception include any oral contraceptive pill, any intrauterine device, any long term
 contraceptive implant, and any long-acting contraceptive injection
- Have been involved in another medicinal trial (CTIMP) within past four weeks.

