4.4 Participant Withdrawal

Each participant must be informed that participation in the trial is voluntary and that he/she may withdraw from the trial at any time and that withdrawal of consent will not affect his/her subsequent medical treatment or relationship with the treating clinician. The investigator(s) or sponsor may withdraw participants from the trial only if indicated by safety/clinical issue or trial protocol. Participants that discontinue azithromycin will not repeat the HROM trial but will be asked to complete all other trial processes such as questionnaires and spirometry if they are willing and have consented to do so. Participants who decline a second HROM trial after their initial trial will be asked to complete all other trial processes if they are willing and have consented to do so.

Participants should remain in the trial for follow-up unless they request to fully withdraw. All data up to the point of withdrawal should be stored. Participants who choose to withdraw or who complete will be invited to complete a short anonymous survey (Appendix B: Trial Experience Survey) to determine their experience of trial participation and any reasons for withdrawal.

In the event of participant withdrawal, the investigator(s) will promptly explain to the participant that their involvement in the trial will discontinue and explain why. The patients' treating clinician will provide medical treatment and/or other necessary measures deemed appropriate by the usual clinician or the participant. This information will be recorded in the CRF. If a participant loses capacity to consent to trial procedures during the trial period, they will be withdrawn from the study. Any data already collected from their participation may be used in the final analysis.

Participants who discontinue early from the trial treatment and/or follow-up will do so for one of the following primary reasons: AE(s), participant deterioration of disease, participant death, lost to follow-up, participant withdrew consent, significant protocol violation. Trial discontinuation information will be documented on the participants CRF.

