7.4 Baseline Assessment Visit (Day 0)

Participants will be invited to attend the Respiratory Medicine Clinical Trials Unit at Castle Hill Hospital for baseline assessment visit within 1 month of screening. Participants who have not had an HROM performed within 3 months prior to screening will also undertake their initial HROM investigation during this visit.

Baseline Assessments:

- Medical history
- Review of previous laboratory results (provided they have been performed as part of routine clinical care in the 3 months prior to recruitment):
 - o Blood Haemoglobin level
 - Total blood white cell count
 - Total blood eosinophil count
 - Blood alanine transaminase
 - Blood alkaline phosphatase
 - Blood bilirubin level
 - o Blood albumin level
 - Sputum microscopy, culture, and sensitivity results.
- Physical examination
- Monitoring of vital signs
- Weight and height
- Electrocardiogram
- Spirometry
- BSCC
- HARQ
- MRC Dyspnoea Scale
- St George's Respiratory Questionnaire
- Disease-specific symptom questionnaires
- Disease-specific quality of life questionnaires
- Cough Visual Analogue Scale
- Monitoring of cough frequency using the Hyfe Cough Tracker
- Initial HROM investigation as per the HROM protocol in section 6, performed by a clinical scientist specialising in GI physiology.

*All individuals undergoing screening will be asked to complete an anonymous survey ('Invitation Experience Survey':) whether they consent to take part in the trial or not. If participants agree to complete the questionnaire this will be taken as implied consent for the information they provide in the survey to be used for the purposes of this study. This survey will be completed with the help of a member of the trial team and stored in the site file.

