7.5 Follow-up Visit (Day 28 to 42)

Participants will be asked to attend for follow-up assessments at 28-42 days after initiation of azithromycin therapy. The participants will undertake a full follow-up assessment and will also have a full review of their condition, including healthcare utilisation, side effects from azithromycin treatment, and experience of HROM investigation.

Follow-up assessment:

- physical examination
- Vital signs
- Electrocardiogram
- Spirometry
- BSCC
- HARQ
- MRC Dyspnoea Scale
- St George's Respiratory Questionnaire
- Cough Visual Analogue Scale
- Disease-specific symptom questionnaires
- Disease-specific quality of life questionnaires
- Monitoring of cough frequency using the Hyfe Cough Tracker©
- Follow-up HROM investigation as per the HROM protocol in section 6, performed by a clinical scientist specialising in GI physiology.
- SAE/ AE reporting
- Health care utilisation recording
- Evaluation of usual care received
- Trial experience survey

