13.3 Discontinuation/Withdrawal of Participants from Study

Each participant has the right to withdraw from the study at any time. In addition, the investigator may discontinue a participant from the study at any time if the investigator considers it necessary for any reason including:

Pregnancy

- Ineligibility (either arising during the study or retrospective having been overlooked at screening)
- Significant protocol deviation
- Significant non-compliance with treatment regimen or study requirements
- An adverse event, which requires discontinuation of the study medication or results in an inability to continue to comply with study procedures
- Consent is withdrawn
- Lost to follow up
- Loss of participant mental capacity to follow the trial protocol

If the participant withdraws consent, no further trial activity will occur, and any samples will be destroyed and the reason for withdrawal will be recorded in the CRF.

As part of the consent process the participant will be asked if all data collected up until the time of withdrawal can be used as part of the study results. If the participant is withdrawn due to an adverse event, the investigator will arrange for follow-up visits or telephone calls until the adverse event has resolved or stabilised. Their data may still be used for analysis.

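### Section 9.1.2 ends adverse event reporting at the ineligibility decision without exempting participants who have already had a trial HROM or started azithromycin

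*Protocol*

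**What the plan says.** The general rule in Protocol section 9.1.2 is: "The AE reporting period for this trial begins when the participant has consented to the trial and ends at the participant's final trial visit". The same section then makes an exception for a consented patient whose ineligibility is discovered later: "then the reporting period will end at the point that the decision was made that the patient was ineligible". Nothing in the exception refers to screening, to HROM or to azithromycin.

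Section 13.3 lists, among the reasons for which the investigator may discontinue a participant, "Ineligibility (either arising during the study or retrospective having been overlooked at screening". Section 4.4 states the general retention rule: "Participants should remain in the trial for follow-up unless they request to fully withdraw".

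Two exposures fall inside the period. At the Day 0 visit (section 7.4), participants without an HROM in the three months before screening "will also undertake their initial HROM investigation during this visit". For azithromycin, section 7.5 sets the end of observation: "Participants will be asked to attend for follow-up assessments at 28-42 days after initiation of azithromycin therapy".

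**The concern.** The exception makes sense for someone who consents, fails screening and is never exposed to anything. As worded, it also covers someone whose ineligibility comes to light after an invasive procedure or after weeks on the drug. For that person, collection of new AEs stops on the day of the decision, while every other participant is observed to the final visit.

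What is at stake is the completeness of the trial's safety data. Section 11 places adverse events among the primary feasibility outcomes, and section 9.2.1 gives the sponsor an ongoing review of risk and benefit. Several exclusion criteria, such as contraindications to HROM, plausibly exist to protect the patient. Events in people entered despite such a criterion are of particular interest to that review.

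**Working it through.** The protocol states no figure on this point, so the check sets its sections side by side.

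1. **Scope of the cut-off (9.1.2).** It applies to any consented patient later found ineligible and takes effect at the decision. It has no exposure condition.

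2. **Can the decision come after exposure?** Yes, for three reasons.
   - Section 13.3 foresees ineligibility arising during the study or overlooked at screening.
   - The schedule of assessments rechecks the criteria at Day 0, the visit at which the initial HROM is done.
   - The flow chart lists the criteria again at Day 28–42, when participants are already on azithromycin. The schedule table does not repeat them there. A decision at that last visit costs little, because reporting ends then for everyone. The entry matters because it shows eligibility being assessed in exposed participants.

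3. **Possible routes.**
   - An HROM attempt at Day 0 fails because of an anatomical abnormality. That meets the section 4.2 criterion, "Unable to be investigated with HROM due to contraindications such as anatomical abnormalities or diseases of the oesophagus", after the procedure has been attempted.
   - Recent long-term macrolide use, or another cardiorespiratory cause of the symptoms (both in section 4.2), is discovered during treatment.

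4. **Does another section restore collection of new events?**
   - Section 9.1.2 keeps SAR and SUSAR reporting going, but says so only for withdrawal of consent to data processing.
   - Section 9.1.2 also follows AEs until they resolve or a decision is made to stop. This covers events already recorded.
   - Section 9.1.1 requires all azithromycin SUSARs to be reported. It provides no contact through which later events would be found, and it does not cover harms of HROM.
   - Section 13.3 arranges follow-up contacts for participants withdrawn because of an AE, not for ineligibility.

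   None of these restores collection of new AEs after the decision.

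5. **Consistency with other rules.** Section 4.4 keeps participants in follow-up unless they ask to withdraw fully. Section 9.3 keeps a pregnant participant in follow-up for trial outcomes. The AE definition in section 9.1 depends on having received a medicinal product and does not mention eligibility.

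6. **Loss per affected participant.** Inputs are the 28 to 42 day visit window (section 7.5) and d, the number of days from the start of azithromycin to the decision. Reporting time lost = (28 to 42) − d.
   - d = 0: 28 to 42 days, the whole window. A failed HROM at Day 0 is this case if follow-up is counted from Day 0.
   - d = 14 (illustrative): 28 − 14 = 14 to 42 − 14 = 28 days.
   - d = 28: 28 − 28 = 0 to 42 − 28 = 14 days.

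   With 30 participants planned, each one affected is 1/30 = 3.3% of the sample. The protocol gives no rate of ineligibility after consent, so no total can be calculated.

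**The case against.** The best defence is that the sentence was meant for screen failures. AE reporting starts at consent, and section 7.2 completes eligibility screening after consent, so some rule is needed for people who consent and then fail. Section 9.1.2 marks the sentence as an exception to its general rule. Section 4.4 also allows the investigator or sponsor to withdraw participants for safety or clinical reasons or under the protocol, and discontinuation for ineligibility in section 13.3 is discretionary. That intention is plausible, and it makes the conflict with section 4.4 a poor fit rather than a flat contradiction. But the wording does not carry the restriction, and a site applying it literally would stop collection in exposed participants.

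The existing safeguards also stand. Recorded AEs are followed, azithromycin SUSARs are reportable, section 9.1.1 refers to a safety SOP that is not shown, and the usual clinician prescribes azithromycin and continues care. The gap is therefore in the trial's recording of new events, not in clinical care.

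A reader might infer three stronger things that the protocol does not support:

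- **That any oesophageal disease seen on the Day 0 HROM makes the participant ineligible.** Section 4.2 concerns people unable to undergo HROM. Section 6.2 treats manometric diagnoses such as achalasia, and hiatus hernia, as study measurements. A completed HROM with an abnormal result is not clearly an exclusion; a failed attempt is the better example.
- **That participants typically leave just after exposure.** That is the worst case. An exclusion found after weeks on treatment leaves most of the window observed.
- **That the AE outcome is biased downward.** This would require participants found ineligible to stay in the safety denominator, and the protocol does not say whether they do.

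**Conclusion.** The point holds as a defect in the wording of section 9.1.2. The cut-off has no exposure condition, section 13.3 confirms that it can apply after exposure, and no other section brings back collection of new events.

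The loss is at most the full 28 to 42 days for an affected participant, and less the later the decision is made. This rests on reading the sentence literally and on counting follow-up from Day 0 or the start of azithromycin. How many of the 30 would be affected cannot be estimated; any count, or any total of participant-days, would be an assumption.

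The consequence is incomplete capture of adverse events. Section 11 names these as a primary feasibility outcome, although the outcome lists in sections 2 and 6.1 do not. The expected size is probably small, but the correction is simple and should be made.

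**What to change.** In section 9.1.2, limit the early end of reporting to patients found ineligible before any trial HROM, including an attempted one, and before azithromycin starts. For anyone already exposed, continue AE and SAE recording to the same end date as for other participants, subject to their consent, whatever their eligibility status. State that these participants are included in the safety summary. Reconcile sections 4.4, 9.1.2 and 13.3 so that all three say the same about follow-up after a late finding of ineligibility.

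The cost is about two sentences of protocol text with matching edits in the other two sections, and an AE contact for what is likely to be a few participants. The change concerns safety data collection only and leaves treatment decisions with the usual clinician.

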9.2 Assessment of SAE's

Severity	The assessment of severity of an SAE will be based on the investigator's clinical judgement using the following definitions:
Assessed by the Co-I and PI or just PI	 Mild: An event that is easily tolerated by the trial subject, causing minimal discomfort, and not interfering with everyday activities. Moderate: An event that is sufficiently discomforting to interfere with normal everyday activities. Severe: An event that prevents normal everyday activities.
Seriousness	An event is considered serious if it meets one or more of the following criteria: (a) results in death
Assessed by the Co-I and PI or just PI	(b)life-threatening (c) requires hospitalisation or prolongation of existing hospitalisation (d) results in persistent or significant disability or incapacity (e) consists of a congenital anomaly or birth defect. Important medical events that may not be immediately life-threatening or result in death or hospitalisation but may jeopardise the patient or may require intervention to prevent one of the outcomes listed in the definition above should also be considered serious.

	Additionally, the investigator must assess whether the AE is unexpected (ie. not listed in the trial protocol as an expected occurrence).
Causality Assessed by the Co-I and PI or just PI	The investigator will assess whether the SAE is likely to be related to the IMP according to the following definitions: • Unrelated : Where an event is not considered to be related to the IMP. • Possibly related : The nature of the event, the underlying medical condition, concomitant medication, or temporal relationship make it possible that the SAE has a causal relationship to the study drug.
Expectedness	To assess expectedness, the R&D Director will need to check if the SAR is listed in the Reference Safety Information (RSI).
Assessed by the R&D Director (on behalf of the Sponsor) for single-site trials	The RSI for IMPs with a marketing authorization (MA) is section 4.8 (Undesirable Effects) of the MHRA approved Summary of Product Characteristics (SmPC) or for IMPs without an MA, the RSI is the relevant section in the Investigator Brochure (IB).
	If the SAR is listed in the RSI then it is expected. If the event is not listed in the RSI then it is unexpected and is a SUSAR and subject to expedited reporting to the MHRA and REC.

9.2.1 Reporting Serious Adverse Events

All SAEs (except those defined as not requiring expedited reporting – see section 8.2.2) will be reported to the Sponsor using the study specific SAE report form, within 24 hours of the research staff becoming aware of the event. For SAE's, the following information will be collected:

• Full details in medical terms and case description

- Event duration (start and end dates, if applicable, and if admitted, admission and discharge dates, with specialty noted)
- Action taken
- Outcome
- Seriousness criteria
- Causality (ie. related or unrelated to the intervention)
- Whether the event would be considered expected or unexpected (this assessment is made by the Sponsor).

Assessment of severity, seriousness and causality will be made by the PI or another authorised study doctor. The PI or authorised study doctor will need to decide whether the serious event is an SAE or SAR by assessing whether the event is either unrelated or possibly related to the IMP (causality). If the event is possibly related then it is a SAR, and an assessment needs to be made by the Sponsor as to whether the event is expected or not for the IMP. If the SAR is listed in Section 4.8 of the MHRA approved Summary of Product Characteristics then it is expected.

In addition to the PI, the Sponsor will also be required to assess causality and document their assessment on the SAE form. The Sponsor must assess causality after the PI and must confirm that they have not influenced the PI. The PI's assessment of causality must not be downgraded by the Sponsor.

If an authorised study doctor from the reporting site is unavailable, initial reports without the causality assessment will be submitted to the Sponsor by a healthcare professional within 24hours of becoming aware of the SAE but will be followed-up by medical assessment as soon as possible thereafter. The PI must always review the SAE form and sign to confirm the contents of the report are accurate and complete and that he/she has also assessed the severity, seriousness, and causality of the SAE.

Any change of condition or other follow-up information should be reported to the Sponsor using the study specific SAE follow-up form as soon as it becomes available. Events will be followed up until the event has resolved or a final outcome has been reached. The PI is required to assess causality again on the follow-up form. If the PI has a change of opinion on causality after considering the additional follow-up information, the Sponsor will be required to reassess causality and if a SAR, then to assess expectedness.

All SAEs assigned by the PI or authorised study doctor as possibly related to IMP-treatment and those the Sponsor has assessed as unexpected will be classified as SUSARs and will be subject to expedited reporting to the MHRA.

Responsibilities

The responsibilities regarding AE and AR reporting as follows:

Principal Investigator (PI):

1. Checking for AEs and ARs when participants attend for treatment / follow-up.

- 2. Using medical judgement in assigning severity, seriousness, and causality.
- 3. Ensuring that all SAEs and SARs are recorded and reported in line with the requirements of the protocol and SUSARs are recorded and reported to the Sponsor within 24 hours of becoming aware of the event and provide further follow-up information as soon as available. Ensuring that SAEs and SARs (including SUSARs) are chased with Sponsor if a record of receipt is not received within 2 working days of initial reporting.
- 4. Ensuring that AEs and ARs are recorded and reported in line with the requirements of the protocol.
- 5. Preparing the clinical sections and final sign off of the Development Safety Update Report (DSUR).

Sponsor:

A medical R&D Director will assess causality and expectedness of behalf of the Sponsor:

- 1. Clinical oversight of the safety of patients participating in the trial, including an ongoing review of the risk/benefit.
- 2. Using medical judgement in assessing, causality of SAEs.
 - 3. In order to assess expectedness, the R&D Director will need to check if the SAR is listed in the Reference Safety Information (RSI). If the SAR is listed in the RSI then it is expected. If the event is not listed in the RSI then it is unexpected and is a SUSAR and subject to expedited reporting to the MHRA and REC.
 - 4. Immediate (within 24 hours) review of all SUSARs.
 - 5. Review of specific SAEs and SARs in accordance with the trial risk assessment and protocol as detailed in the Trial Monitoring Plan.
 - 6. Central data collection and verification of AEs, ARs, SAEs, SARs and SUSARs according to the trial protocol.
 - 7. Reporting safety information to the Sponsor Oversight Group for the ongoing assessment of the risk / benefit according to the Trial Monitoring Plan.
 - 8. Expedited reporting of SUSARs to the Competent Authority (MHRA in UK) and REC within required timelines.
 - 9. Notifying Investigators of SUSARs that occur within the trial.
 - 10. The unblinding of a participant for the purpose of expedited SUSAR reporting.
 - 11. Checking for (annually) and notifying the PI of updates to the Reference Safety Information for the trial.
 - 12. Preparing standard tables and other relevant information for the DSUR in collaboration with the PI and ensuring timely submission to the MHRA and REC.

Unexpected SAE's related to the intervention will be reported to the MHRA, Research Ethics Committee that gave a favourable opinion of the trial and the sponsor (Hull University Teaching Hospitals NHS Trust R&D department) within 7 days of the principal investigator becoming aware of the event using the electronic SUSAR (eSUSAR) reporting form available from: https://esusar.mhra.gov.uk/ Any additional relevant information must be sent within 8 days of the initial report.

A SUSAR which is not fatal or life-threatening must be reported to the MHRA and REC as soon as possible and no later than **15 days** after learning of the event.

